# **Clear Conversations:**

## **Evaluating a Verbal Health Literacy intervention in Derbyshire**

### **1. Background**

#### **1.1 Health Literacy**

Health Literacy is important so that everyone has the ability to access and receive high quality healthcare (WHO 2014). Health literacy has been defined as a person's ability to understand and use information to make decisions about their health so they can 'be active partners in their care' (NHS England, 2024). People with low Health Literacy struggle to read and understand health information, communicate with health professionals, know how to act on the information they receive, and know what health services to use and when to use them (Osborne *et al.*, 2013).

#### **1.2 Health literacy and health inequalities**

There is a link between socioeconomic deprivation and low Health Literacy. That is, those with lower Health Literacy are more likely to be from socially deprived areas and have no educational qualifications (Roberts, 2015).

Low Health Literacy is associated with:

- Unhealthy lifestyles and poorer general health
- Low use of preventative services e.g. vaccinations and screening
- Increased attendance at A&E and hospital admissions
- Decreased life expectancy

(NHS 2023. NIHR, 2022, Roberts, 2015).

If Health Literacy is improved this can positively affect treatment adherence, and lead to reduced numbers of call backs, cancelled appointments and improved satisfaction and outcomes (Roberts, 2015). It has been suggested that interventions to improve Health Literacy will best be targeted at those with lower levels of

education, those living in the most deprived areas, and those with a limiting health condition or disability (Roberts, 2015).

### **1.3 The context of this study**

#### **1.3.1 Joined Up Care Derbyshire**

Across Derby and Derbyshire three out of nine areas and six out of ten people are estimated to be below the UK average for Health Literacy and numeracy (JUCD, 2024). Joined Up Care Derbyshire (JUCD) is one of 42 Integrated Care Systems in England. It brings together NHS, local authorities, and the voluntary sector to deliver better care to whole communities, both adults and children, in Derbyshire (<https://joinedupcarederbyshire.co.uk/>). It aims to improve Derbyshire's population life expectancy and healthy life expectancy levels, compared to other parts of the country, and reduce health inequalities.

JUCD has a Stay Well Initiative which includes Quality Conversations, Personalisation and Health Literacy. JUCD offers free Quality Conversations training to all staff. They also provide information and training resources to staff via their website on Personalised Care and Health Literacy. JUCD appointed a Health Literacy Officer in 2022. This is a role that it is not commonly seen in Integrated Care Systems in the UK.

#### **1.3.2 Quality Conversations**

Quality Conversations is an evidenced based communications skills programme for staff, developed by the Derbyshire Psychological Insights team and Public Health Derbyshire, to support the implementation of Making Every Contact Count in Derbyshire (Pennell, 2023). It is informed by Michie et al's (2011) COM-B behaviour change model (Michie et al., 2011) and is focused on addressing health inequalities through '*compassionate and curious conversations*' (Pennell, 2023). The training sessions for staff are delivered by professional coaches and '*supplemented with a suite of localised support, web-based resources, an ambassador network and team-based sessions to embed the approach and ensure sustainably of learning*' (Pennell, 2023).

### 1.3.3 The Health Literacy Officer role

The Health Literacy Officer role aims to implement Health Literacy initiatives throughout the JUCD system. The officer works with organisations and teams within JUCD to support them to take evidence-based steps to provide more Health Literacy friendly services. The initial focus of the role has been on written communication.

The Health Literacy Officer has supported teams to reduce the average reading age of their services' information materials from 18 years of age to 9 across 19 services. These changes have received positive feedback from both staff and patients. Now the focus is turning to how to embed Verbal Health Literacy techniques into services.

### 1.3.4 Verbal Health Literacy interventions - The evidence base

Improving health professionals' health literate communication skills is important and has the potential to positively impact on person centred prevention activities and healthcare, by reducing Health Literacy demands (Connell *et al.*, 2023; Kaper *et al.*, 2019; Murugesu *et al.*, 2022). Evidence suggests that effective health conversations can potentially increase adherence to treatment, patient safety, quality of life and health outcomes (Kaper *et al.*, 2019, Connell *et al.*, 2023).

NHS England and Scotland both advocate the use of good communication, both spoken and written, to help address Health Literacy issues (Public Health England, 2023; NHS Scotland, 2023). In their Health Literacy toolkits and guides they recommend the use of:

- Simple language (NHS Scotland, 2023).
- Teach-back techniques (Health Education England, NHS England and Public Health England, 2023; NHS Scotland, 2023). A method of making sure patients understand the health information they receive (Yen and Leasure 2019),
- Chunk and check techniques (Health Education England, NHS England and Public Health England, 2023; NHS Scotland, 2023). Where information is broken down into smaller chunks rather than giving it all at once. Then

checking it is understood before moving onto the next 'chunk' (NHS Scotland 2023).

- Pictures and visual aids (NHS Scotland, 2023).

A recent study in the USA explored the patient-surgeon encounter using audio-recordings and a post encounter survey (Rainey *et al.*, 2022). They found that improving communication by slowing speech, using more understandable words, and intentionally allowing more time for patients to speak and ask questions were immediately actionable ways to improve patient understanding (Rainey *et al.*, 2022).

A number of studies and literature reviews have explored the use of Verbal Health Literacy techniques (Kaper *et al.*, 2019; Murugesu *et al.*, 2022; Talevski *et al.*, 2020; Yen & Leasure, 2019). However, there are few UK studies exploring this issue.

Teach-back specifically has been shown to be effective in improving learning related outcomes. These outcomes include knowledge recall and retention and health related outcomes such as hospital re-admissions and quality of life (Talevski *et al.*, 2020). The Teach-back method was recommended by 99% of those using it (Murugesu *et al.*, 2022) and was considered to be quick and cost effective (Talevski *et al.*, 2020). However, there were inconsistent results related to Teach-back, with regards to knowledge retention, and implementation into routine practice was rarely considered (Talevski *et al.*, 2020). A training session on Teach-back alone was not considered to be adequate for translation into practice to occur or be sustained (Talevski *et al.*, 2020; Yen & Leasure, 2019). This indicates the need for additional implementation support. In addition, there was a lack of studies using comprehensive health literacy outcome measures (Larsen *et al.*, 2022) or patient centred outcomes (Walters *et al.*, 2020).

One UK qualitative study undertaken in Staffordshire focused on community pharmacy (Cork & White, 2022). Pharmacists received a one-off training session on Teach-back, chunk and check and the use of simple language and visual aids. They were given two months to use it in practice before giving their perceptions of its usefulness in a semi-structured interview. Key findings included:

- Health professionals would have preferred more time to practice the techniques with patients.
- They found chunk and check harder to use than Teach-back and felt it was better for longer rather than short consultations.
- Visual aids were useful.
- It was easy to slip back into jargon and habitual use of more complicated language.

(Cork & White, 2022).

This highlights the need to continue to evaluate Health Literacy interventions, particularly those aimed at improving Verbal Health Literacy. It also highlights the need to explore additional implementation support, and measurement of outcomes and experiences over a longer time period.

#### 1.3.5 The intervention to be evaluated

The intervention is a Verbal Health Literacy techniques training package for staff. Its purpose is to enable clearer health conversations. It has been developed using insights gained from the well-established Quality Conversation programme currently available to all healthcare and public health staff in Derbyshire. The Verbal Health Literacy training is a two hour interactive and experiential session. The main focus is on how staff can learn, practice and implement three key Verbal Health Literacy techniques: 'simple language', 'Teach-back' and 'chunk and check'. This is complemented with Health Literacy Officer support for implementation of the techniques into practice. The support is tailored to the individual service staff's needs.

#### 1.3.6 The services where the intervention will be used

The intervention will be used in two very different services.

1. Live Life Better Derbyshire tier 2 weight management services (Public Health, Derbyshire County Council). The aim of the programme is to help people lose weight. The service provides online and face to face group education and advice programmes that run for one session a week over a rolling 12 week period. The programmes have an accompanying website and resources. The

programme is available for all people in Derbyshire. Eight Public Health Improvement Advisors (HIA's) offer advice to groups of up to 25 people who need to lose weight. 33 programmes run across Derbyshire, 19 online and 14 face to face. Attenders are followed up at 12, 26 and 52 weeks and a weight maintenance programme is available.

2. Derbyshire Community Health Service Pulmonary Rehabilitation programme provided within the NHS. The aim of the programme is to improve people's exercise tolerance and respiratory health. This service provides a six week rolling face to face programme that runs across 6 venues in Derbyshire. 15 members of staff, a mixture of physiotherapists, healthcare assistants and specialist nurses, offer supervised exercise and education and advice to people who are limited by their respiratory condition in Derbyshire. The physiotherapists and specialist nurses lead the sessions and have most contact with patients. Up to 12 people attend two sessions a week over the six week period which are a combination of exercise and education.

#### 1.3.7 The proposed Theory of Change

For the Live Life Better Derbyshire service, the training will help staff to communicate in simpler language and check service users' understanding of actions they need to take. This will help service users to understand what they need to do to lose weight, be activated to self-manage their weight, take actions to lose weight, and adhere to the 12 week programme. This will help them to lose weight and maintain weight loss.

For the Pulmonary Rehabilitation service, the training will help staff communicate in simpler language and check service users' understanding of the actions they need to undertake. This is so service users will understand what they need to do to improve their exercise tolerance and respiratory health, be more likely to take actions, and thus improve their overall health. It is hoped the intervention will also help activate people to continue to manage their own physical and respiratory health beyond the programme and know what to do should they suffer an acute exacerbation.

## **2. Research question and aims & objectives**

### **2.1. Research question**

Can a Verbal Health Literacy training intervention for health workers improve health outcomes and reduce health inequalities for people using their services?

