### **2.3. Objectives**

- a) To understand staff perceptions of the acceptability and feasibility of the Verbal Health Literacy training session, and the support to use the techniques in practice from the Health Literacy Officer.
- b) To understand staff knowledge of the Verbal Health Literacy techniques and their confidence and skills to use them.
- c) To understand how the Verbal Health Literacy techniques taught in the training session are being actioned in practice.
- d) To determine whether subjective Health Literacy and activation skills, such as the ability to self-manage, engage with healthcare services and understand what actions to take, are improved for service users after attending programmes delivered by Verbal Health Literacy trained members of staff.
- e) To measure the impact of the Verbal Health Literacy training on health and wellbeing outcomes.
- f) To describe the Index of Multiple Deprivation quintile of attendees at programmes and compare with the Derbyshire population in order to assess impact on health inequalities.

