### **3.5. Assessment of individual service user health and wellbeing outcomes**

The two services collect a range of data about service user outcomes. For the weight management programme service users complete routine service assessments at baseline12 and 26 weeks. For the pulmonary rehabilitation programme assessments are carried out at baseline and on completion of the programme at six weeks. That is after attendance at 8-12 sessions. This is so change can be measured over time.

The researcher will seek consent to access this data for all those service users who attend either of the two participating programmes during the intervention period.

This data will be available at individual service user level if service users give informed consent. This data is stored on the services databases. Only anonymised data will be shared with the researcher.

Additional anonymised demographic data of attendees, that is routinely collected by the services, will be shared with the researcher. This data will include gender, ethnicity, age and index of multiple deprivation.

Primary and secondary outcomes for each of the two participating services will be collected. The outcomes are:

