### For both services

- Attendance numbers
- Did Not Attend (DNA) numbers and programme completion rates.
- Summarised demographic data of attendees to include numbers and % by gender, ethnicity, age group and index of multiple deprivation quintile.

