### LLBD weight management programme

- Mean weight and standard deviation at baseline, 12 weeks and 26 weeks
- Mean weight loss and standard deviation between baseline and 12 weeks, and between baseline and 26 weeks.
- Mean score on the short form Warwick and Edinburgh Mental Health and Wellbeing Scale and standard deviation at baseline and 12 weeks.
- Mean change in the short form Warwick and Edinburgh Mental Health and Wellbeing Scale and standard deviation between baseline and 12 weeks s.

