#### 3.10.4 Individual service user outcome data

##### LLBD Weight Management Programme

For the individual level outcome data, the analysis will be descriptive, displaying mean weight loss, mean short form Warwick Edinburgh score, and mean scores for the Health Literacy Questionnaire domains at the three time points. Then multiple regression will be used to test differences in changes in means between baseline and 12 weeks in the trained and untrained groups. We will also consider whether people who had an improvement in the Health Literacy Questionnaire domains were more likely to have better outcomes.

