#### 3.10.5 Aggregate service data

For the aggregated outcome data we will compare mean change in an outcome in a three month period before the training and in the three month period after the training for trained and untrained groups. Means and standard deviations will be provided by the services, that is, no individual data will be shared with researchers.

To meet the final objective, we will compare the IMD quintiles for attendees at the programmes in the three month period post-training with the IMD quintiles for the IRAS 336469

Derbyshire population. The expectation is that the % of people in socially deprived quintiles will be higher for the programmes than for the Derbyshire population.

SPSS and Excel spreadsheets will be used to store, organise and assist in analysis of the quantitative data from multiple sources.

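### The research question asks about reducing health inequalities among service users, but the plan assesses inequality only by who attends, not by who benefits

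*Combined protocol and SAP*

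**What the plan says.** All references are to the combined protocol and SAP.

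- **Research question (Section 2.1).** Training is to "improve health outcomes and reduce health inequalities for people using their services". The aim in Section 2.2 mentions health outcomes only.
- **Objective f (Section 2.3), the one that addresses inequalities.** "To describe the Index of Multiple Deprivation quintile of attendees at programmes and compare with the Derbyshire population in order to assess impact on health" (the quote stops one word short of the end of the objective).
- **Matching analysis (Section 3.10.5), with the county as comparator.** "we will compare the IMD quintiles for attendees at the programmes in the three month period post-training with the IMD quintiles for the" (the sentence then names the county's residents). The anticipated result is stated: "The expectation is that the % of people in socially deprived quintiles will be higher for the programmes than for the Derbyshire population".
- **Individual data (Section 3.5).** For consenting users, IMD comes with the demographic data: "This data will include gender, ethnicity, age and index of multiple deprivation".
- **Individual weight analysis (Section 3.10.4).** "multiple regression will be used to test differences in changes in means between baseline and 12 weeks in the trained and untrained groups". No covariate, subgroup or interaction is named.
- **Service-level request (Section 3.7).** IMD is requested as "Summarised demographic data of attendees to include numbers and % by gender, ethnicity, age group and index of multiple deprivation quintile". Outcomes are requested as whole-group summaries, for example "Mean weight loss and standard deviation between baseline and 12 weeks, and between baseline and 26 weeks". The two are not crossed. Sections 3.7 and 3.10.5 both say that no individual records will be shared for this part.

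**The concern.** For people already using a service, the natural meaning of reducing inequality is that the difference in outcome between more and less deprived users becomes smaller. Nothing in the plan estimates that difference or how training changes it.

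The analysis that is planned answers another question. Comparing attendees with the county population shows whether the programmes reach deprived people. It uses only the post-training period and does not separate trained from untrained groups, so its anticipated result could appear whether or not training did anything. It cannot attribute even a change in reach to the training.

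This matters on the plan's own rationale. Section 1.2 ties low health literacy to deprivation and suggests that interventions are best aimed at the most deprived areas, so a training effect that differs by deprivation is part of the premise. Section 8 expects commissioners to use the findings when deciding on funding. They would receive an average effect and an attendee profile, and neither says who gained.

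**Working it through.** **Inputs from the documents.** Mean 12-week weight loss 4.7 kg v 4.3 kg, so a difference of 0.4 kg; SD 1.6; 252 per group; 80% power; 5% significance; about 330 users per group who can be invited (all Section 3.9.3). About 160 consenting users per group (Section 3.9.2). Eight advisors, four trained (Section 3.2).

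**Assumption.** The documents do not give the share *p* of users in the more deprived band (quintiles 1-2, say). I use 0.2 and 0.4.

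**1. The plan's own figure.** For two means, two-sided:

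n = 2 × (1.960 + 0.842)² × 1.6² / 0.4² = 2 × 7.85 × 16 = 251.2, rounded up to 252 per group.

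This reproduces. It is sized for one overall difference.

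**2. What an average can conceal.** Hold the average training effect at 0.4 kg and let the deprived band gain nothing. The others then gain 0.4 / (1 − p):

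- p = 0.2: 0.4 / 0.8 = 0.50 kg
- p = 0.4: 0.4 / 0.6 = 0.67 kg

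Because the deprived band gains zero, that is also how far the gap widens. The overall comparison still shows 0.4 kg, as it would if everyone gained 0.4 kg, and the attendee IMD profile is unchanged.

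**3. Precision if the missing estimate is added.** For the difference in training effect between bands, with n per group:

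SE = 1.6 × √[(2/n) × (1/p + 1/(1 − p))]; 95% half-width = 1.96 × SE.

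The bracket 1/p + 1/(1 − p) is 4.167 at p = 0.4 and 6.25 at p = 0.2.

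| n per group | p | SE (kg) | Half-width (kg) |
|---|---|---|---|
| 160 (consented individual data) | 0.4 | 0.365 | 0.72 |
| 160 | 0.2 | 0.447 | 0.88 |
| 330 (aggregate data) | 0.4 | 0.254 | 0.50 |
| 330 | 0.2 | 0.311 | 0.61 |

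**4. Power for the illustrated widening at 160 per group**, as Φ(widening/SE − 1.96):

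- p = 0.4: Φ(0.667/0.365 − 1.96) = Φ(−0.13), about 45%
- p = 0.2: Φ(0.50/0.447 − 1.96) = Φ(−0.84), about 20%

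These figures treat users as independent, as the plan's calculation does. Users are grouped under eight advisors, so the true intervals are likely to be wider. The 330-per-group rows describe the post-training trained v untrained contrast; also subtracting the 2023 contrast would widen them.

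**The case against.** **The plan does have an inequalities analysis.** Objective f says what it will do, and Section 3.10.5 does it. The authors may mean inequality as reach: an average benefit delivered to a more deprived group of attendees. Section 2.1 names no gap and no estimand, and the aim in Section 2.2 is silent on inequality. This stands to a degree: it would be wrong to say that inequality is ignored. But reach is narrower than the wording of Section 2.1, and the comparison lacks the contrast needed to credit training with reach.

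**The regression might include IMD.** Section 3.10.4 does not list covariates, so IMD is unspecified, not excluded. Adjusting for it would still give a single average training effect.

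**The added estimate would be weak.** This stands. At 160 per group the half-width exceeds the illustrated widening at both assumed shares (0.72 v 0.67 kg; 0.88 v 0.50 kg). That argues for an exploratory estimate with its interval, not for leaving part of the research question unanswered.

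**Stronger readings that the documents do not support.**

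- A reader might infer that a widening gap would be reported as a success. No success rule is set. A positive mean difference with a deprived attendee mix would meet the expectations in Sections 3.9.2 and 3.10.5, but success is an inference from that.
- A reader might infer that a widening could never be seen. Section 3.5 supplies individual outcomes and IMD for consenting users, so it could be examined there later. Only the aggregate data, as requested, rule it out. Specifying the analysis now guards against selective reporting.
- A reader might fault the pulmonary rehabilitation regression for lacking the same interaction. That service has no untrained group (Section 3.2), so there is no trained v untrained effect to vary by deprivation.

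**Conclusion.** The concern holds as a mismatch between question and analysis. Section 2.1 asks about inequalities among users; the plan measures only who attends, and after training only. No planned figure, sample size or test becomes wrong.

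On the plan's own 0.4 kg average, a gap widening of 0.50-0.67 kg could sit behind the reported result. That rests on an assumed deprived share of 20-40% and on the assumption that this band gains nothing. It illustrates what the planned analyses cannot distinguish; it is not a prediction.

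Outcome by IMD is recoverable from the consented individual data but not from the aggregate data as now requested. The change is worth making before extraction, provided that the result is presented as an estimate of limited precision.

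**What to change.** **(a) Section 3.10.4, weight management.** Add a training-by-IMD term to the 12-week change regression (quintiles 1-2 v 3-5, or a trend across quintiles). Report the training effect in each band, and the difference between bands with a 95% CI, labelled exploratory. State that an inconclusive interval does not show equal benefit.

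**(b) Section 3.7, before the services extract anything.** Request number, mean change, SD and completion by IMD band, for each group and period. For pulmonary rehabilitation, report the 2023 and 2024 CRDQ change by band descriptively only: there is no untrained group, and Section 3.9.2 expects only about 72 consenting users.

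**(c) Sections 2.1 and 2.3.** State that objective f measures reach only. Then either answer the inequalities part of Section 2.1 with (a) and (b) as exploratory, or limit Section 2.1 to reach.

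**Cost.** Part (a) is one model term on data already planned. Part (b) asks the services to produce an additional split, which the documents do not show to exist already, and small cells may be suppressed. Part (c) is a wording change. The main statistical drawback is wide intervals, before any allowance for clustering by advisor.
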